5.7 Diet/Activity/Other Considerations

5.7.1 Diet

Subjects should maintain a normal diet unless modifications are required to manage an AE such as diarrhea, nausea or vomiting.

5.7.2 Contraception

MK-3475 may have adverse effects on a fetus *in utero*. Furthermore, it is not known if MK-3475 has transient adverse effects on the composition of sperm. Non-pregnant, non-breast-feeding women may be enrolled if they are willing to use 2 methods of birth control or are considered highly unlikely to conceive. Highly unlikely to conceive is defined as (1) surgically sterilized, or (2) postmenopausal (a woman who has not had menses for greater than 1 year will be considered postmenopausal (and this will be confirmed by FSH testing)),

or (3) not heterosexually active for the duration of the trial. The two birth control methods can consist of two barrier methods or a barrier method plus a hormonal method to prevent pregnancy. Subjects should start using birth control from the screening visit throughout the study period up to 120 days after the last dose of study drug or until the last blood draw (for non-treated controls).

The following are considered adequate barrier methods of contraception: diaphragm, condom (by the partner), copper intrauterine device, sponge, or spermicide, as per local regulations or guidelines. Appropriate hormonal contraceptives will include any registered and marketed contraceptive agent that contains an estrogen and/or a progestational agent (including oral, subcutaneous, intrauterine, or intramuscular agents).

Subjects should be informed that taking the study medication may involve unknown risks to the fetus (unborn baby) if pregnancy were to occur during the study. In order to participate in the study they must adhere to the contraception requirement (described above) for the duration of the study and during the follow-up period defined in section 7.2.2.

If there is any question that a subject will not reliably comply with the requirements for contraception, that subject should not be entered into the study.

5.7.3 Use in Pregnancy

If a subject inadvertently becomes pregnant while on treatment with MK-3475, the subject will immediately be removed from the study. The site will contact the subject at least monthly and document the subject's status until the pregnancy has been completed or terminated. The outcome of the pregnancy will be reported to the Sponsor without delay and within 24 hours if the outcome is a serious adverse experience (e.g., death, abortion, congenital anomaly, or other disabling or life-threatening complication to the mother or newborn). The study investigator will make every effort to obtain permission to follow the outcome of the pregnancy and report the condition of the fetus or newborn to the Sponsor. If a male subject impregnates his female partner the study personnel at the site must be informed immediately and the pregnancy reported to the Sponsor and followed as described above and in section 7.2.2.

5.7.4 Use in Nursing Women

It is unknown whether MK-3475 is excreted in human milk. Since many drugs are excreted in human milk, and because of the potential for serious adverse reactions in the nursing infant, subjects who are breast-feeding are not eligible for enrollment.

5.8 Subject Withdrawal/Discontinuation Criteria

Subjects may withdraw consent at any time for any reason or be dropped from the trial at the discretion of the investigator should any untoward effect occur. In addition, a subject may be withdrawn by the investigator or the Sponsor if enrollment into the trial is inappropriate, the trial plan is violated, or for administrative and/or other safety reasons. Specific details regarding discontinuation or withdrawal procedures; including specific details regarding withdrawal from Future Biomedical Research, are provided in Section 7.1.4 – Other Procedures.

Discontinuation from treatment is “permanent”. Once a subject is discontinued, he/she shall not be allowed to restart treatment.

A subject must be discontinued from the trial for any of the following reasons:

- The subject or legal representative (such as a parent or legal guardian) withdraws consent.
- For subjects who have declined a study-prescribed pre-treatment core needle biopsy but instead have undergone a diagnostic biopsy performed as per local SOC from which tissue will be submitted, this biopsy was not performed within 45 days prior to the first dose of MK-3475 or tissue submitted is not sufficient for the specified study-related analyses.
- The subject, if randomized to receive neoadjuvant MK-3475, interrupts neoadjuvant trial medication administration for more than 7 consecutive days or 1 cumulative missed dose.
- The subject has a medical condition or personal circumstance which, in the opinion of the investigator and/or Sponsor, places the subject at unnecessary risk through continued participation in the trial or does not allow the subject to adhere to the requirements of the protocol.
- The subject has a confirmed positive serum pregnancy test.
- In subjects assigned to receive neoadjuvant MK-3475, histologic analysis of the pre-treatment core needle biopsy does not confirm the diagnosis of RCC with one or more clear cell components present.
- In all subjects, histologic examination of the surgically excised tumor tissue does not confirm the diagnosis of RCC with clear cell elements.
- In subjects assigned to receive neoadjuvant MK-3475, the patient does not undergo surgical RCC resection within 5 weeks of the final dose of MK-3475.

- In subjects assigned to the control group (no neoadjuvant MK-3475), the patient fails to undergo surgical RCC resection within 6 weeks of randomization.
- The subject has not recovered from surgical RCC resection and therefore does not begin post-resection MK-3475 within 60 days of surgery.

Note: Exception if Sponsor approves a longer interval between surgery and the start of post-resection MK-3475

- In subjects with metastatic disease at the time of RCC resection, radiologic disease progression is confirmed by local site assessment during post-resection MK-3475 administration.

Note: Such subjects should be managed by irRECIST, with PD confirmed as outlined in Section 5.8.1.

Note: Exception if Sponsor approves treatment continuation (Section 5.8.1)

- In subjects without metastatic disease at the time of RCC resection, metastatic or locally recurrent disease is confirmed by local site assessment during post-resection MK-3475 administration.

Note: Exception if Sponsor approves treatment continuation (Section 5.8.1)

- Unacceptable adverse experiences as described in Section 5.2.1.2 Dose Modification.
- Intercurrent illness that prevents further administration of treatment.
- Investigator decides to withdraw the subject.
- Noncompliance with trial treatment or procedure requirements.
- The subject is lost to follow-up.
- The subject has completed 17 administrations (approximately 1 year) of post-resection MK-3475 treatment.
- Administrative reasons

The End of Treatment and Follow-up visit procedures are listed in Section 6 (Protocol Flow Chart) and Section 7.1.5 (Visit Requirements). For those subjects receiving MK-3475, following the final dose of study drug, each subject will be followed for 30 days for adverse event monitoring (serious adverse events will be collected for 90 days after the end of MK-3475 treatment as described in Section 7.2.3.1).

Subjects who discontinue for reasons other than disease progression will have post-treatment follow-up for disease status until disease progression, initiating a non-study cancer treatment, withdrawing consent or becoming lost to follow-up. After documented disease progression each subject will be followed by telephone for OS until death, withdrawal of consent, or the end of the trial, whichever occurs first.

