5.2.1.2 Dose Modification and Toxicity Management Guidelines for Pembrolizumab

Dose modification and toxicity management for immune-related AEs associated with pembrolizumab

AEs associated with pembrolizumab exposure may represent an immunologic etiology. These immune-related AEs (irAEs) may occur shortly after the first dose or several months after the last dose of pembrolizumab treatment and may affect more than one body system simultaneously. Therefore, early recognition and initiation of treatment is critical to reduce complications. Based on existing clinical trial data, most irAEs were reversible and could be managed with interruptions of pembrolizumab, administration of corticosteroids and/or other supportive care. For suspected irAEs, ensure adequate evaluation to confirm etiology or exclude other causes. Additional procedures or tests such as bronchoscopy, endoscopy, skin biopsy may be included as part of the evaluation. Based on the severity of irAEs, withhold or permanently discontinue pembrolizumab and administer corticosteroids. Dose modification and toxicity management guidelines for irAEs associated with pembrolizumab are provided in [Table 6](#) for neoadjuvant dosing and [Table 3](#) for post-resection dosing.

5.2.1.2.1.1 Neoadjuvant MK-3475

Based on the first interim analysis of lymphocytic infiltrates in tumors resected from the first 9 subjects, if an increase in tumor lymphocytic infiltration of 2-fold or greater is not observed in more than one of the 6 subjects in this group that received a 2 dose course of neoadjuvant

MK-3475, all subsequent subjects enrolled in this trial may be treated with 3 doses of MK-3475. Details are described in Section 8.0 – Statistical Analysis Plan.

Administration of neoadjuvant MK-3475 during this trial must be discontinued for drug-related toxicities above Grade 1 in severity and for severe or life-threatening AEs as described in Section 5.6.1. Such subjects should proceed with SOC surgical RCC resection as soon as they have sufficiently recovered from the AE to undergo this procedure.

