For subjects without metastatic disease at the time of surgical RCC resection who experience drug-related toxicities above Grade 1 during neoadjuvant treatment, post-resection MK-3475 should also not be administered and the subject should be permanently discontinued. However, subjects with known metastatic disease at the time of surgical RCC resection who develop Grade 2 or greater drug-related AEs during neoadjuvant MK-3475 treatment may still be eligible to receive post-resection MK-3475 if the drug-related AE severity as listed in [Table 3](#) below does not prescribe permanent treatment discontinuation.

5.2.1.2.1.2 Post-Resection MK-3475

Post-resection administration of MK-3475 must be withheld for drug-related toxicities and severe or life-threatening AEs as per [Table 3](#) below. See Section 5.6.2 for supportive care guidelines, including use of corticosteroids to be followed during post-resection administration of MK-3475 (only applicable in the Post-Resection Phase of the study).

Table 3 Dose Modification and Toxicity Management Guidelines for Immune-related AEs Associated with Pembrolizumab (During Post-Resection Phase ONLY)

| General instructions: | | | | |
|------------------------------|---|--------------------------------------|---|--|
| Immune-related AEs | Toxicity grade or conditions (CTCAEv4.0) | Action taken to pembrolizumab | irAE management with corticosteroid and/or other therapies | Monitor and follow-up |
| Pneumonitis | Grade 2 | Withhold | 
 Administer corticosteroids (initial dose of 1-2 mg/kg prednisone or equivalent) followed by taper | 
 Monitor participants for signs and symptoms of pneumonitis Evaluate participants with suspected pneumonitis with radiographic imaging and initiate corticosteroid treatment Add prophylactic antibiotics for opportunistic infections |
| | Grade 3 or 4, or recurrent Grade 2 | Permanently discontinue | | |

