7.1.4 Other Procedures

7.1.4.1 Withdrawal/Discontinuation

The investigator or trial coordinator must notify the Sponsor when a subject has been discontinued/withdrawn from the trial. If a subject discontinues for any reason at any time during the course of the trial, at the time of discontinuation or as soon as possible after discontinuation depending upon the phase the subject is in, the subject may be asked to return to the clinic (or be contacted) for a discontinuation visit as outlined for Post-operative Follow Up visit or Discontinuation visit/30 Day Follow-up in Section 6.0 – Trial Flow Charts to have the applicable procedures conducted. The investigator should perform a follow-up phone call 90 days after the last dose of trial drug to determine if any SAEs/ECIs have occurred since the discontinuation visit. Any AEs which are present at the time of discontinuation/withdrawal should be followed in accordance with the safety requirements outlined in Section 7.2 - Assessing and Recording Adverse Events.

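### The missed-dose removal rule conflicts with the toxicity rules for metastatic subjects, and removal makes the visit that captures 30-day surgical complications discretionary

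*Combined protocol and SAP*

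**What the plan says.** **Removal rule (Section 5.8).** The list opens with "A subject must be discontinued from the trial for any of the following reasons". One entry is a subject assigned to neoadjuvant drug who "interrupts neoadjuvant trial medication administration for more than 7 consecutive days or 1 cumulative missed dose". That entry has no exception, although several later entries allow one with Sponsor approval. The section also states: "Once a subject is discontinued, he/she shall not be allowed to restart treatment".

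**Toxicity rules (Section 5.2.1.2.1.1 and Table 5).** "Administration of neoadjuvant MK-3475 during this trial must be discontinued for drug-related toxicities above Grade 1 in severity". Then: "Such subjects should proceed with SOC surgical RCC resection as soon as they have sufficiently recovered from the AE to undergo this procedure". Subjects without metastatic disease receive no post-resection drug and are permanently discontinued. Those with known metastatic disease "may still be eligible to receive post-resection MK-3475", provided Table 3 does not call for permanent discontinuation. Table 5 gives premedication for exactly this case after a Grade 2 infusion reaction.

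**Third rule (Section 7.1.1.8).** Interruptions of neoadjuvant drug go to a documented joint decision of investigator and Sponsor.

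**Follow-up.** Sections 7.1.5.5 and 7.2.3.3 call for surgical complications within 30 days of surgery to be assessed and recorded in all subjects, at a visit 30 to 42 days after surgery. For a discontinued subject, Section 7.1.4.1 says that "the subject may be asked to return to the clinic (or be contacted) for a discontinuation visit". Section 8.2.4 lists surgical complications under Primary Safety and contrasts them with published rates.

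**The concern.** A subject with drug-related toxicity above Grade 1 after dose 1 must stop neoadjuvant drug, so dose 2 is missed and the Section 5.8 entry is met. In metastatic disease one section then removes the subject with no restart, while another leaves on-trial drug open after surgery. Sites would have to choose, and could choose differently.

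The statistical stake is the first primary objective, the safety of neoadjuvant drug in patients who go on to resection. Subjects with toxicity before surgery matter for that question, and once removed they are the ones for whom the visit that captures surgical complications becomes discretionary. Section 7.1.4.1 also times the discontinuation visit at discontinuation or soon after, depending on phase. It could therefore fall before surgery and miss the complications altogether.

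**Working it through.** **1. The plan's own figures.** Table 13 is 1 − (1 − p)^n. For p = 5% this gives 70.8% at n = 24 and 81.6% at n = 33 (stated: 71 and 82). All 15 cells reproduce to within half a point. The 80% upper bound with no event is 1 − 0.20^(1/n): 6.49% at 24 and 4.76% at 33 (stated: 6 and 5). This point disputes none of these figures.

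**2. The rules side by side**, for toxicity above Grade 1 with a planned dose still to come:

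| | Section 5.8 | Section 5.2.1.2.1.1 and Table 5 | Compatible? |
|---|---|---|---|
| No metastases | Removed, no restart | Resection, no further drug, permanently discontinued | Yes |
| Metastatic | Removed, no restart | Resection, post-resection drug possible | No |

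Toxicity after the last planned dose causes no missed dose and does not trigger the conflict.

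**3. Which data are exposed.** Day 0 is the last neoadjuvant dose. Adverse events are collected to day 30 (Sections 5.8 and 7.2) and serious events to day 90 (Section 7.2.3.1). Surgery is planned 2 to 3 weeks after the last dose (Section 7.1.5.4), with a 5-week limit in Section 5.8. Postoperative days inside the adverse event window = max(0, 30 − surgery day).

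| Surgery day | 30-day postoperative window ends | Days covered, of 30 | Visit falls on days |
|---|---|---|---|
| 14 | 44 | 16 | 44–56 |
| 21 | 51 | 9 | 51–63 |
| 35 | 65 | 0 | 65–77 |

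All three postoperative windows end before day 90, so serious complications remain collected unless new anticancer therapy starts. Non-serious complications, and the laboratory and vital-sign data of the postoperative visit, are not protected.

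**4. How many subjects.** The documents give no rate of drug-related Grade 2 or higher events between doses. Let q be the share missing a dose for toxicity, assumed 5% to 25%. The expected number is nq, and the chance of at least one is 1 − (1 − q)^n.

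| q | n = 24: expected; chance of ≥1 | n = 33: expected; chance of ≥1 |
|---|---|---|
| 5% | 1.2; 71% | 1.7; 82% |
| 11% | 2.6; 94% | 3.6; 98% |
| 25% | 6.0; >99% | 8.3; >99% |

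These counts include subjects with and without metastases; the share who are metastatic is not given.

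**5. Effect if all these subjects lost their postoperative data.** At n = 24, between 23 (q = 5%) and 18 (q = 25%) remain. The chance of seeing a complication with a 5% rate falls from 70.8% to between 69.3% and 60.3%, and the zero-event bound rises from 6.5% to between 6.8% and 8.6%. At n = 33, between 31 and 25 remain, and the chance falls from 81.6% to between 79.6% and 72.3%.

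**6. Possible bias, illustrated.** Take the published complication rate of 27.6% (Section 8.2.4) for unaffected subjects.
- *Lost subjects left out of the denominator.* With q = 11% and an assumed 50% rate among them, the true rate is 0.89 × 27.6 + 0.11 × 50 = 30.1%, against 27.6% seen. If their rate is also 27.6%, there is no bias.
- *Lost subjects kept in the denominator and counted as event-free.* With 27.6% in everyone, the rate seen is 0.89 × 27.6 = 24.6%. This is an extreme, because serious complications would still be reported.

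**The case against.** **Section 5.8 defers to the toxicity rules.** Its list has a separate entry for unacceptable adverse experiences that refers to Section 5.2.1.2, so the missed-dose entry may be meant for compliance-type interruptions, the subject of Section 7.1.1.8. That reading is reasonable, but it is not written down. Each entry suffices by itself for removal, and the toxicity entry does not disapply the missed-dose entry.

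**The rules mostly agree.** This stands. A reader might infer that the two sections cannot both be followed for any subject with toxicity. The documents do not support that: subjects without metastases are discontinued under both, and removal from the trial does not prevent standard-of-care surgery.

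**Safety data are kept.** This largely stands. A reader might infer that subjects with toxicity lose their primary safety data. They do not. Section 8.2.3 keeps everyone with at least one dose in the safety population. Adverse events are collected for 30 days and serious events for 90, a 90-day call is planned, and events present at discontinuation are followed. Sections 7.1.5.5 and 7.2.3.3 speak of all subjects, and Section 7.1.4.1 allows contact instead of a visit. What remains is that the provision specific to discontinued subjects is discretionary, and no text says that the general one overrides it.

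**The size is unknown.** This stands. The 11% and 18% in Section 4.2.1.5 are Grade 3–5 events of any attribution in metastatic melanoma, over exposure through two or three doses. Grade 2 drug-related events would add to them; unrelated events and events after the last planned dose would subtract. On the three-dose path the first six subjects receive two doses, so even this proxy gives 6 × 0.11 + 27 × 0.18 = 5.5 of 33.

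**Conclusion.** The contradiction is real and unresolved for metastatic subjects whose drug-related toxicity above Grade 1 falls before a remaining planned dose. Confidence in this is high.

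The data consequence is narrower and less certain. In any dosed subject removed this way, with or without metastases, non-serious surgical complications and postoperative visit data could go uncollected. The loss would be linked to toxicity and would touch a component of Primary Safety. About 1 to 6 of 24, or 2 to 8 of 33, would be exposed under the assumed 5% to 25%; how many would actually lose data cannot be derived.

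A reader might infer that the complication rate is biased low. The documents show only that it could be: loss is possible rather than certain, and nothing in them shows that toxicity before surgery raises complication risk. The point should be corrected, but it does not undermine the safety analysis as a whole.

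**What to change.** - Reconcile the missed-dose entry in Section 5.8 with Section 5.2.1.2.1.1, Table 5 and Section 7.1.1.8 so that one rule applies. Which clinical rule is kept is for the sponsor to decide.
- State in Section 5.8, separately, what stops drug and what ends trial participation.
- Amend Section 7.1.4.1 so that the 30-day surgical complication and adverse event assessment, by visit or contact, is required for every subject who received at least one neoadjuvant dose and undergoes resection, including those discontinued, unless consent is withdrawn.

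The cost is protocol wording. The visit is already in the flow charts, and Table 13 and the planned sample sizes do not change.

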| Tissue Collection | Fresh tumor tissue for shipping (TIL analysis, histoculture, tumor cell isolation and IMR expression analysis) | | | | | | X | |
| | Tumor tissue for FFPE (IHC; DNA for mutational analysis, TCR utilization, promoter methylation analysis; RNA for gene expression and miRNA analysis) | | | X ^u | | | X ^{v,w} | |
| | Fresh tumor tissue for snap freezing (DNA isolation, metabolic profiling, laser capture microdissection) | | | | | | X | |
| | Fresh non-malignant kidney tissue from resected tumor specimen for snap freezing (DNA isolation) | | | | | | X | |
| | Fresh tumor tissue in RNAlater solution (RNA extraction, gene expression) | | | | | | X | |
| | Fresh non-malignant kidney tissue in RNAlater solution (RNA extraction, gene expression) | | | | | | X | |
| Blood | PBMC Phenotypic Analysis | | | X ^t | | | X ^q | X |
| | PBMC Isolation and Cryopreservation (Antigen-specific T cell response evaluation) | | | X ^t | | | X ^q | X |
| | Plasma (miRNA, and exosome evaluation) | | | X ^t | | | X ^q | X |
| | Serum (biomarkers) | | | X ^t | | | X ^q | X |
| | Serum (PK/PD) | | | | X ^x | X ^y | X ^q | X |
| | RNA isolation (gene expression, miRNA expression) | | | X ^t | | | X ^q | X |
| | DNA isolation (TCR utilization) ^z | | | X ^t | | | X ^q | X |
| | B cell isolation and transformation | | | | | | | |
| Urine for exosome isolation and analysis | | | | X ^t | | | X ^{aa} | X |

- a. Randomization, initially 2:1 neoadjuvant MK-3475:controls. Randomization will occur only after written consent is obtained and will occur after all screening assessments have been completed. Randomization can occur at any time point after screening and prior to core biopsy.
- b. This follow up visit must occur no less than 30 days after the day of SOC tumor resection.
- c. Written consent must be obtained prior to performing any protocol-specific procedure. Results of a test performed prior to the subject signing consent as part of routine clinical management are acceptable in lieu of a screening test if performed within 28 days prior to screening.
- d. If the subject signs the FBR consent, leftover samples may be kept for Future Biomedical Research.
- e. Prior medications – Record all medications taken within 28 days of screening visit. Concomitant medications – Enter new medications started during the trial through 30 days after the last dose of trial treatment. Record all medications taken for SAEs as defined in Section 7.2

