For randomized subjects only, AEs that occur from the time the consent is signed through the time of randomization will only be reported as AEs if they are the result of a protocol-specified intervention, including but not limited to washout or discontinuation of usual therapy, diet, placebo treatment or a procedure. All AEs will be recorded from the time of randomization through 30 days following cessation of treatment (for MK-3475 treated patients), or 14 days following the last blood draw (for non-treated controls), and at each examination, on the AE case report forms/worksheets. The reporting timeframe for adverse events meeting any serious criteria is described in section 7.2.3.1. The investigator will make every attempt to follow all subjects with non-serious adverse events for outcome.

Electronic reporting procedures can be found in the Electronic Data Capture (EDC) data entry guidelines. Paper reporting procedures can be found in the Investigator Trial File Binder (or equivalent).

Progression of the cancer under study is not considered an adverse event unless it results in hospitalization or death.

7.2.1 Definition of an Overdose for This Protocol and Reporting of Overdose to the Sponsor

For purposes of this trial, an overdose of pembrolizumab will be defined as any dose of 1,000 mg or greater (≥ 5 x the indicated dose). No specific information is available on the treatment of overdose of pembrolizumab. In the event of overdose, the subject should be observed closely for signs of toxicity. Appropriate supportive treatment should be provided if clinically indicated.

If an adverse event(s) is associated with (“results from”) the overdose of Sponsor's product or vaccine, the adverse event(s) is reported as a serious adverse event, even if no other seriousness criteria are met.

If a dose of Sponsor's product or vaccine meeting the protocol definition of overdose is taken without any associated clinical symptoms or abnormal laboratory results, the overdose is reported as a non-serious Event of Clinical Interest (ECI), using the terminology “accidental or intentional overdose without adverse effect.”

All reports of overdose with and without an adverse event must be reported within 24 hours to the Sponsor either by electronic media or paper. Sponsor Contact information can be found in the Investigator Trial File Binder (or equivalent).

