7.2.3 Immediate Reporting of Adverse Events to the Sponsor

7.2.3.1 Serious Adverse Events

A serious adverse event is any adverse event occurring at any dose or during any use of Sponsor's product that:

- Results in death;
- Is life threatening;
- Results in persistent or significant disability/incapacity;
- Results in or prolongs an existing inpatient hospitalization;
- Is a congenital anomaly/birth defect;
- Is a new cancer (that is not a condition of the study);
- Is associated with an overdose;
- Is an other important medical event

Refer to [Table 11](#) for additional details regarding each of the above criteria.

Progression of the cancer under study is not considered an adverse event unless it results in hospitalization or death.

Any serious adverse event, or follow up to a serious adverse event, including death due to any cause that occurs to any subject from the time the consent is signed through 90 days following cessation of treatment (for MK-3475 treated patients), or 14 days following the last blood draw (for non-treated controls), or 30 days following cessation of treatment if the subject initiates new anticancer therapy, whichever is earlier, whether or not related to the Sponsor's product, must be reported within 24 hours to the Sponsor either by electronic media or paper. Sponsor Contact information can be found in the Investigator Trial File Binder (or equivalent).

Additionally, any serious adverse event, considered by an investigator who is a qualified physician to be related to the Sponsor's product that is brought to the attention of the investigator at any time outside of the time period specified in the previous paragraph also must be reported immediately to the Sponsor.

All subjects with serious adverse events must be followed up for outcome.

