7.2.3.3 Surgical complications

All subjects enrolled in this clinical trial will undergo SOC surgical RCC tumor resection. Control subjects will proceed to surgery without study-related treatment, while patients randomized to receive neoadjuvant MK-3475 will proceed to surgery 2-3 weeks following the final MK-3475 dose. As such, any surgical complications in the intra- and postoperative period (30 days from the time of surgery) will be recorded, and will include but will not be limited to the following:

1. the need for and the volume of blood transfusions in the perioperative period
2. hospital readmission following discharge
3. thromboembolic events
4. cardiovascular events
5. pulmonary complications
6. gastrointestinal complications
7. postoperative infection
8. incision-related complications

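### A neoadjuvant subject whose surgery slips past 5 weeks must leave the trial, so non-serious complications of that surgery can be missed, and no safety summary counts the delay

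*Combined protocol and SAP*

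**What the plan says.** Section 5.8 lists reasons for which a subject must be discontinued from the trial. For the neoadjuvant arm, one is that "the patient does not undergo surgical RCC resection within 5 weeks of the final dose of MK-3475". Some items in the list carry a note allowing a Sponsor-approved exception; this one does not.

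Section 5.2.1.2.1.1 stops neoadjuvant dosing for drug-related toxicity above Grade 1 and then says: "Such subjects should proceed with SOC surgical RCC resection as soon as they have sufficiently recovered from the AE to undergo this procedure". It gives no time limit. For such a subject without metastases, "post-resection MK-3475 should also not be administered and the subject should be permanently discontinued".

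Safety data are collected under several clocks:

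- General AEs (section 7.2): "All AEs will be recorded from the time of randomization through 30 days following cessation of treatment (for MK-3475 treated patients").
- SAEs (section 7.2.3.1): "through 90 days following cessation of treatment (for MK-3475 treated patients"), shortened to 30 days if new anticancer therapy starts. Drug-related SAEs are reportable at any time.
- Surgical complications (section 7.2.3.3, worded for all enrolled subjects): "any surgical complications in the intra- and postoperative period (30 days from the time of surgery) will be recorded". They are assessed at the Post-operative Follow Up visit, 30 to 42 days after resection (section 7.1.5.5). Of that visit the flow chart in 6.1 says: "This follow up visit must occur no less than 30 days after the day of SOC tumor resection".
- After discontinuation (section 7.1.4.1): attendance at a visit is at the site's request. The visit is modelled on either the Post-operative Follow Up or the Discontinuation/30-Day visit, and falls at discontinuation or as soon as possible after it. A call 90 days after the last dose asks about SAEs and ECIs. Section 5.8 adds follow-up for disease status.

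Section 8.2.4 summarises the complication incidence in neoadjuvant subjects against published rates (27.6% overall). Sections 4.2.3.1, 7.2.3.3, 8.2.2 and 8.2.4 do not name surgery delayed or not done. The AE form's action-taken item concerns study drug only (section 7.1.2.1, Table 11).

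**The concern.** The first primary objective is the safety of neoadjuvant MK-3475 in patients going on to resection. A drug reaction that postpones or prevents the operation is a harm particular to this setting. One section asks such a subject to wait until recovered; another removes the subject if the wait is too long.

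Removal takes away the one required visit at which complications are assessed. It does so selectively, in subjects whose surgery was late, including those delayed by toxicity. The complication rate compared with the literature could then under-represent the subjects of most interest. The delay itself would not appear in any planned safety table.

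**Working it through.** **Plan's own figures.** The plan gives no rate of delayed or missed surgery. Its nearest safety figures reproduce. The zero-event limit 1 − 0.2^(1/n) gives 12.55, 10.17, 8.55, 6.49 and 4.76% for n = 12, 15, 18, 24 and 33, which round to the stated 13, 10, 9, 6 and 5%. All 15 cells of Table 13 follow from 1 − (1 − p)^n.

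**Can the two instructions collide?** The limit is 5 × 7 = day 35 after the last dose. The flow chart agrees: surgery is planned three weeks after the last dose, +14 days, so 21 + 14 = 35. For a Grade 3-4 immune-related AE, Table 6 advises a steroid taper over at least 4 weeks, begun after improvement to Grade 1. If surgery waits for the end of the taper (an assumption; the protocol does not require it), improvement later than day 35 − 28 = 7 after the last dose already breaches the limit.

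**What the general windows cover.** Let s be the day of surgery after the last neoadjuvant dose, with no further drug. Of the 30 postoperative days:

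- days in general AE recording = max(0, 30 − s)
- days in SAE recording = min(90, s + 30) − s, for s up to 90, if no new anticancer therapy starts

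| Surgery day s | AE days of 30 | SAE days of 30 |
|---|---|---|
| 14 | 16 | 30 |
| 21 | 9 | 30 |
| 35 | 0 | 30 |
| 36 | 0 | 30 |
| 60 | 0 | 30 |
| 61 | 0 | 29 |
| 75 | 0 | 15 |

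Rows up to day 35 are not a gap for a subject still on trial, because the required postoperative visit supplies the complications separately. The rows that matter are those after day 35. The AE clock closed at day 30, five days before the removal rule applies. No later dose reopens it: discontinuation from treatment is permanent under 5.8, and subjects without metastases who had the toxicity are barred from post-resection drug.

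**Does the discontinuation visit fill the gap?** Surgery on day 36 completes its 30-day period on day 36 + 30 = 66. A visit held at or soon after discontinuation, about day 35, would precede the operation or most of that period. Following AEs already present at discontinuation (section 7.1.4.1) does not help, since complications of an operation not yet done are not present. The day-90 call would reach them only if they were SAEs or ECIs.

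**Effect on the complication rate.** With 24 or 33 subjects dosed (Table 4), one unassessed subject is 1/24 = 4.2 or 1/33 = 3.0 percentage points. As illustration only, assume the assessed subjects have the published 27.6% rate and the unassessed have 50 to 75%:

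- 1 of 24 unassessed: (23 × 0.276 + 1 × 0.50)/24 = 28.5%, up to 29.6% with 0.75.
- 3 of 24 unassessed: (21 × 0.276 + 3 × 0.50)/24 = 30.4%, up to 33.5% with 0.75.

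Both compare with 27.6% among those assessed. With 3 unassessed, the zero-event limit for a complication type rises from 6.49% to 1 − 0.2^(1/21) = 7.38%.

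**The case against.** The strongest reply is that complication capture is tied to surgery, not to the last dose. Section 7.2.3.3 covers all enrolled subjects, section 7.1.5.5 puts the assessment at a visit for everyone, and section 7.1.4.1 names that visit as one model for the discontinuation visit. This stands as a statement of intent: no rule excludes these complications. It does not secure the data, because after removal attendance is optional and timed around discontinuation.

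The remaining gap is also narrow. Complications that cause or prolong hospitalisation are SAEs and run to day 90. The Sponsor is told of every discontinuation, and exclusions from analysis are listed with reasons in the Results Memo (section 8.2.3). In a 36-subject trial individual cases could be traced. That holds too, and limits the point to a modest improvement.

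Several stronger readings are tempting but unsupported:

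- *On-time surgery is under-followed, because only 16 to 9 days of AE recording remain.* A subject operated on by day 35 who remains on trial has the required visit.
- *The 5.8 item for a subject who "interrupts neoadjuvant trial medication administration for more than 7 consecutive days or 1 cumulative missed dose" removes everyone stopped for toxicity.* Section 5.2.1.2.1.1 and Table 5 let subjects with metastases remain eligible for post-resection drug after such a stop, which would be empty on that reading.
- *The toxicity itself is lost.* The AST set keeps every dosed subject, and AEs present at discontinuation are followed.
- *Controls dilute the complication rate once they receive drug.* Section 8.2.4 already restricts that summary to neoadjuvant subjects.
- *Table 13 shows a high chance of at least one case.* Its rates are for serious AEs, not delayed surgery. The 11% and 18% Grade 3-5 figures in 4.2.1.5 come from melanoma and are not delay rates either.

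**Conclusion.** The point holds in a limited form. Under the plan as written, non-serious complications of surgery after day 35, in a neoadjuvant subject who receives no further drug, can be missed; it would be wrong to say they will be. SAEs in the 30 postoperative days are fully covered when surgery is by day 60 and no new anticancer therapy starts, and partly after that (15 of 30 days for surgery on day 75). Surgery delayed beyond 5 weeks or not done because of toxicity appears only as a discontinuation reason, not in a safety summary.

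The number affected is unknown and probably small. Any loss would be selective and would bear on a primary safety summary, at 4.2 or 3.0 percentage points of uncertainty per unassessed subject. The day counts rest on the documents alone. The shifted complication rates rest on assumed values for the unassessed and show scale, not expectation.

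**What to change.** 1. Amend 5.8 and 7.1.4.1 so that missing the 5-week limit removes the subject from the per-protocol PD set and from further study drug, but not from safety follow-up. Require the postoperative complication assessment, by visit or contact, at least 30 days after surgery whenever it takes place.
2. In 8.2.4, among all subjects with at least one neoadjuvant dose, report the number and percentage with surgery more than 5 weeks after the last dose or not done, with the reason. State how many of them had complications assessed.

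The cost is a protocol amendment, a few CRF fields and one routine postoperative contact for a few subjects. Dose, sample size and PD decision rules are unchanged. The count will be imprecise: 0/24 has an exact 95% upper limit of 14.2%, and 2/24 = 8.3% has an interval of 1.0 to 27.0%. It should be read as description only.
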